### 8.4.3 Procedure

For consented subjects that meet the eligibility criteria, record the relevant data regarding their procedure. Record the following procedure information:

- Treatment and control sides
- Length of incisions
- Note: Subjects who require a total knee on one side and a unicompartmental on the other side will not be included in the final analysis and should be exited from the study.

### 8.4.4 Wound Closure Procedure / Protocol

The Zip device placement will be carried out following a standard protocol as described in the Instructions for Use (IFU)

### 8.4.5 Data to be collected at time of procedure and/or prior to discharge:

- Closure Method Satisfaction (Surgeon Rating)

- Pain (Subject Rating) - A 11 point Numerical Rating Scale rating pain from *No Pain (0)* to *Worst Pain Imaginable (10)* will be used to measure general pre and post-operative pain and specific incisional pain.
- Any complications/adverse events
- High resolution digital photographs of any preexisting scar or unusual skin appearance at the incision site and immediately after incision closure (optional)

#### 8.4.6 Data to be collected at follow up visits

While performing the **2 week** follow up visit, record the following information:

- Cosmetic Outcome (Surgeon Rating)
  - Wound Evaluation Scale (WES) – The surgeon will conduct a follow up evaluation of the wound using the WES assessment. The WES evaluates six clinical variables including incision edges, contour irregularity, width, edge inversion, inflammation and overall cosmesis.
- Any complications/adverse events
- Range of Motion Measurements
- High definition photos will be taken of the incision/scar areas.
- Closure Method Comfort (Subject Rating)
  - A 5 point Likert Scale ranging from *Very Comfortable* to *Very Uncomfortable*
- Pain (Subject Rating)
  - A 11 point Numerical Rating Scale rating pain from *No Pain (0)* to *Worst Pain Imaginable (10)* will be used to measure general post- operative pain and specific incisional pain

While performing the **final** follow up visit (between week 6 and week 8), record the following information:

- Range of Motion Measurements (Physical Therapist Ratings)
- Pain (Subject Rating)
  - A 11 point Numerical Rating Scale rating pain from *No Pain (0)* to *Worst Pain Imaginable (10)* will be used to measure general post- operative pain and specific incisional pain
- Cosmetic Outcome (Subject & Surgeon Ratings)
  - Scar Satisfaction - A 5 point Likert Scale ranging from *Very Satisfied* to *Very Dissatisfied*
  - Scar Assessment - A 10 point Visual Analog Scale rating scar cosmesis from *0=Best Expected Scar* to *10=Worst Scar*
  - Wound Evaluation Scale (WES) – The surgeon will conduct a follow up evaluation of the wound using the WES assessment. The WES evaluates six clinical variables including incision edges, contour irregularity, width, edge inversion, inflammation and overall cosmesis.
  - Cosmetic Visual Analogue Scale (CVAS) – High definition photos will be taken of the incision/scar area at the final follow-up visit. Photos will be collected and evaluated using a VAS Scar Score by an objective independent panel (not affiliated with the study site) of up to 5 plastic surgeons.

#### 8.5 Follow-up

The subject should be queried before discharge regarding any discomfort experienced after Zip device and staple use. After removal of both the Zip device and staples the status of the wounds should be assessed. Any Adverse Events should be noted. These data will be captured on the Case Report Forms. High resolution digital photographs should be taken after closure device removal (day 14) and at final 6 or 8 week follow-up visit. A user survey will be provided and will be required to be filled out as part of the follow-up.

Scar / cosmetic appearance will be evaluated on a visual analogue scales (CVAS). Physician and patient satisfaction with the closure techniques and the scar appearances will be evaluated.

## **8.6 Study Exit**

Once the subject has completed the final follow-up visit or has withdrawn early, they should be exited from the study. The date of exit and subject status should be recorded on the Case Report Form.

# **9 Statistical Considerations**

## **9.1 Analysis Populations and Data Handling Conventions**

### **9.1.1 Effectiveness Intent-to-Treat (ITT) Population**

All subjects will be included in effectiveness ITT analyses according to the randomized order of patients for treatment assignments, including the dermal closure procedure, regardless of protocol deviations.

### **9.1.2 Effectiveness Per Protocol Population**

The effectiveness per protocol population includes all subjects completing Zip Surgical Skin Closure and standard dermal closure (Staple) treatments per protocol. The analysis will be performed according to the actual treatments received, including the dermal closure procedure.

### **9.1.3 Safety**

All subjects who receive any portion of the Zip Surgical Skin Closure treatment or control (staple) treatment will be included in safety analysis and analyzed by actual treatment received.

### **9.1.4 Missing Data**

Missing or loss data will not be included in the analysis.

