## 1 ZIPS Study- Trial Protocol Synopsis

|                                 |   |
|---------------------------------|---|
| Study Title                     | ZIPS Study - Zip Incision aPproximation vs. Staple
A prospective, randomized controlled post-market study to compare the use of the Zip® Surgical Skin Closure Device versus conventional staples for skin closure in subjects having undergone bilateral knee arthroplasty – Protocol No. 006  |
| Overall Objective               | The objective of this study is to evaluate the Zip Surgical Skin Closure device versus conventional steel staple placement when utilized for surgical wound closure after bi lateral unicompartmental (UNI) or bi lateral total knee replacement (TKA).   |
| Study Device                    | ZipLine Medical Inc., Zip Surgical Skin Closure Device  |
| Indication for Use              | The Zip Surgical Skin Closure Device is indicated for use during and after skin incision procedures to approximate skin and hold together the skin edges until healing can take place.  |
| Study Design                    | A prospective, non-blinded, randomized, within patient control study. A total of up to 25 subjects (targeted min. n=22) requiring bilateral knee arthroplasty (unicompartmental or total) will be enrolled. Each subject will serve as their own control, since one knee closure will be with staples, and the other knee closure with Zip device. The order of patients will be randomized to receive Zip device on one knee and steel staples on the opposing knee. |
| Number of Subjects              | A total of up to 25 patients (serving as their own control) will be enrolled. There is anticipated patient fall out (screen failures) post procedure due to surgeon not knowing which procedure is required (total or unicompartmental) until time of surgery.  |
| Number of Sites                 | ≤ 3   |
| Duration of Study               | Each enrolled subject will be followed until 6 to 8 weeks post-procedure.   |
| Primary Effectiveness Endpoints | Wound healing as judged by the CVAS (Cosmetic Visual Analogue Scale) wound healing scale – From photos taken between 6 to 8 weeks post op visit – to be judged by panel of Plastic Surgeon blinded to treatment assignments.   |

|                                   |  |
|-----------------------------------|--|

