### **3.3 Risks and Benefits**

#### **3.3.1 Risks**

Complications that may occur include:

- Allergic response
- Infection
- Dehiscence requiring intervention
- Device failure / malfunction
- Edema
- Wound site pain / discomfort
- Excessive scarring including:
  - Step-off
  - Contour irregularities
  - Excessive distortion
  - Poor cosmetic appearance

Previous evaluations have not shown any additional risks in comparison to those associated with existing wound closure methods.

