### 6.2 Withdrawal of Subjects

Subjects may withdraw from the study at any time, with or without reason and without prejudice to further treatment. In all cases of withdrawal, the reason(s) for withdrawal (if given) will be recorded upon study termination.

In addition, the investigator may withdraw the subject due to any of the following situations:

- adverse event;
- any other reason determined by the investigator to be in the best interest of the subject.

Subjects withdrawn due to an adverse event should be followed until the event has been resolved or is stable, if at all possible.

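### A subject withdrawn for an adverse event can leave without the photographs behind the primary CVAS, and no analysis checks the effect of the lost pair

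*Combined protocol and SAP*

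**What the plan says.** The synopsis gives the source of the primary CVAS: "From photos taken between 6 to 8 weeks post op visit". Section 8.4.6 agrees: "High definition photos will be taken of the incision/scar area at the final follow-up visit". An independent blinded panel scores the photographs.

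Section 6.2 states that "the investigator may withdraw the subject due to any of the following situations", and an adverse event is the first reason listed. For those subjects it asks only this: "Subjects withdrawn due to an adverse event should be followed until the event has been resolved or is stable, if at all possible". Section 8.6 adds: "Once the subject has completed the final follow-up visit or has withdrawn early, they should be exited from the study". Neither section asks for the final photographs of a withdrawn subject.

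The whole missing-data rule, in section 9.1.4, is: "Missing or loss data will not be included in the analysis". Section 9 contains no imputation, tipping-point or other missing-data sensitivity analysis. The synopsis treats the study as complete for the primary endpoint once 22 subjects have had the 6 to 8 week visit, with enrolment capped at 25.

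**The concern.** The primary test is a paired t test, so a subject without final photographs loses the whole pair. Loss unrelated to the between-knee difference costs only power. Loss that depends on the difference shifts the mean of the pairs that remain, and the within-patient design gives no protection because the selection acts on the difference itself.

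A link of that kind is plausible here. The risks in section 3.3.1 include infection, poor cosmetic appearance and "Dehiscence requiring intervention". A wound event on one knee could lead to withdrawal and also leave that knee with the worse scar. The study is "A prospective, non-blinded, randomized, within patient control study", so the person deciding on withdrawal knows which closure is on the affected knee.

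The comparison would then lean towards the closure whose poor results are missing. With 22 to 25 pairs, a few such losses could matter, and the plan has no analysis that would show whether they did.

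**Working it through.** **Inputs.** From section 9.3: SD about 1.5 (taken as the SD of the paired differences), difference 1.0, alpha 0.025, power 90%, target 22 pairs. From section 9.2.2: one-sided paired t test. From the synopsis: cap of 25, completion at 22. The number, side and size of the losses are my assumptions, as no rate is given. Differences are Zip benefit over staples, so positive favours Zip.

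**The plan's own figure.** The normal approximation gives n = (1.5 × (1.960 + 1.282) / 1.0)² = 23.6, so 24 pairs. The exact paired t needs 26. Exact power at 22 pairs is 84.6%, against the stated 90%. The present point does not depend on this, but there is little power to spare.

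**Zip-side losses with no true difference.** Suppose all 25 pairs average 0 and k lost pairs each equal -v. The retained n = 25 - k pairs then average kv/n, and the noncentrality is kv / (1.5 × √n). For k = 3, v = 2: n = 22, mean 6/22 = 0.273, noncentrality 0.853, critical t 2.080, rejection probability 12.6%. The last row is a simulation from normal(0, 1.5) that deletes the k lowest of 25 differences, with 1,000,000 runs per cell.

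| One-sided error (nominal 2.5%) | 1 lost | 2 lost | 3 lost |
|---|---|---|---|
| Random loss | 2.5% | 2.5% | 2.5% |
| Each lost pair is -1 | 3.4% | 4.5% | 6.0% |
| Each lost pair is -2 | 4.5% | 7.7% | 12.6% |
| Worst pairs for Zip always lost (upper bound) | 7.0% | 14.2% | 23.4% |

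If one pair is lost on each side, the error stays at 2.5% for equal and opposite pairs. It is 4.2% if the most extreme pair on each side is always the one lost.

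**Staple-side losses with a true difference of 1.0.** Random loss of 1, 2 or 3 pairs leaves power of 87.8%, 86.3% or 84.6%. If the best pairs for Zip are always lost, power is 82.6%, 74.4% or 65.0%.

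**Illustrative tipping point.** Assume 22 observed pairs with mean 0.8 and SD 1.5. The standard error is 1.5/√22 = 0.320, t = 2.50, one-sided p = 0.0104. The critical t on 21 df is 2.080, so significance needs a mean of at least 2.080 × 0.3198 = 0.665. Hold that standard error and critical value, and let k missing pairs average x:

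(22 × 0.8 + kx) / (22 + k) = 0.665, so x = [0.665 × (22 + k) - 17.6] / k.

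This gives x = -2.3 for one missing pair, -0.8 for two and -0.3 for three.

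Entering the missing pairs as if observed, at one common value, is not a sound substitute. At the observed mean of 0.8, one, two or three such entries improve p from 0.0104 to 0.0079, 0.0059 or 0.0044, because n rises and the SD shrinks. That version's tipping values are -1.95, -1.06 and -0.73. It overstates robustness with two or three losses, and understates it with one.

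**The case against.** The strongest reply is that the route is unlikely to be used often. Withdrawal under 6.2 is discretionary, and nothing makes a wound complication a trigger. Section 8.1 expects participation to run to the final visit. Section 9.2.3 accumulates adverse events to that visit, and 13.1 sets a monitoring period of 3 months. Table 1 ties the visit to the surgeon's own schedule. Both closures are off by about day 14, so little treatment is left to stop. Adverse events also include systemic ones that favour neither knee. All of this stands and lowers the likely number of losses. None of it requires the photographs.

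The plan also reports disposition (8.4.2), completes exit forms for everyone enrolled (section 10), and may hold 14-day photographs and surgeon WES. These help to describe a loss, but they do not replace the 6 to 8 week panel score. The per-protocol set is defined by completing the closures, so it does not test the missing-data assumption either.

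A reader might infer that the open design biases the CVAS scores themselves. The documents do not support that, because the panel is blinded; the open design bears here only on who is withdrawn. A reader might also infer a bias in favour of Zip. The text gives no direction: Zip-side losses would flatter Zip, and staple-side losses would work against it.

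**Conclusion.** The gap is in the current text: the exit and exclusion rules allow an adverse-event withdrawal to remove a primary pair, and nothing shows whether the conclusion survives. It is minor.

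The size is conditional on assumed one-sided losses. One Zip-side loss at -1 or -2 moves the error from 2.5% to 3.4% or 4.5%; three move it to 6.0% or 12.6%. The figure of about 23% should not be read as the trial's error rate, because it needs three losses that are always the three worst pairs for Zip. Three losses also use the entire margin from 25 to 22, which mixed-procedure exits (5.1) share.

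Nor do the documents support reading this as a fatal flaw. They do not say that withdrawn subjects must miss the final visit, and event follow-up may in practice reach it.

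**What to change.** 1. **Main change, sections 6.2 and 8.6.** State that withdrawal for an adverse event does not end outcome collection. Unless consent is withdrawn, the 6 to 8 week photographs of both knees are still taken and sent to the blinded panel. This changes no clinical decision on withdrawal.

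2. **Secondary change, section 9.1.4.** Keep the complete-pair t test. Report missing pairs by reason and affected side. Pre-specify one tipping-point analysis on the paired difference that does not treat imputed pairs as observed data. Either shift the assumed mean of the missing pairs while holding the complete-case standard error and critical value, or use multiple imputation with a shift. Report the value at which significance at 0.025 is lost, beside the range of observed differences. Working on the difference needs no score for either knee, so it applies when both photographs are missing.

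The cost is a few sentences, a few photographs at a visit already scheduled, and one extra analysis. Some withdrawn subjects will still decline, which is why the second change is worth having. The tipping point does not correct the estimate; it shows only how unfavourable the missing pairs would have to be.

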## **9.2 Statistical Analysis Plan**

### **9.2.1 General Summary**

CVAS summary statistical results will include, averages standard deviation, range, and Coefficient of Variation (CVs) will be reported for both the control and treatment. Results will include significance testing (t test) with calculated p value(s). Graphic representation of data with distribution analysis of CVAS results will also be presented and summarize. All variables of interest including subject demographics, baseline characteristics, effectiveness and safety endpoints will be summarized.

### **9.2.2 Effectiveness**

#### **11.2.2.1. Primary Effectiveness Analyses**

There is one primary endpoint for the study, i.e. Cosmetic Visual Analogue Scale (CVAS) for incision appearance at the final (6 to 8 week) follow-up evaluation for gathering CVAS scores. The purpose is to reveal superior cosmesis results of Zip device in comparison to standard staple closure. The sample size determined, per Section 7, for this study is up to 25 patients.

#### **CVAS**

The hypothesis for cosmesis is that use of the Zip Surgical Skin Closure device will result in CVAS results that are significantly superior to standard staples administered. A 1-sided paired “t” test will be performed to reject the  $H_0$  with >95% confidence. Alpha Error for the 1-sided test = 0.025.

The assumption (hypothesis) for CVAS is:

$H_0$ : Zipline CVAS scores will not be superior to CVAS scores for staples.

$H_A$ : Zipline CVAS scores will be superior to CVAS scores for staples.

Since CVAS scores are measured on a 0 – 10 Likert scale for quality of closure, a distribution analysis will also be performed with summary statistics to show that the incisions closed with the Zip devices result in a cosmetically superior scar as compared to the incisions closed with staples.

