### 8.2 Enrollment

Subjects that meet the inclusion/exclusion criteria will be invited to participate in the study and sign the Institutional Review Board (IRB) or Ethics Committee (EC) approved informed consent form. All subjects must provide written informed consent before undergoing any study related activity.

Subjects that meet all the eligibility criteria will be enrolled in the study and will serve as their own control. Subjects will be randomized in a 1:1 ratio to receive both the Zip device treatment and the staples on each knee.

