**Table 1. Study Event Schedule**

|  | Before Procedure | Uni/TKA Procedure-Zip device or staple control Placement | Discharge 0-3 days Post Procedure | 14 days (+/-1 week) post Procedure | 6-8 weeks** (+/-4 days) post Procedure |
|--|------------------|--|-----------------------------------|------------------------------------|--|
| Study Initiation:  | X                |  |                                   |                                    |  |
| Informed Consent   | X                |  |                                   |                                    |  |
| Demographics/ Medical History  | X                |  |                                   |                                    |  |
| Clinical Status evaluation/site evaluation prior to wound closure device placement | X                |  |                                   |                                    |  |
| Inclusion / Exclusion Criteria Assessment  | X                |  |                                   |                                    |  |
| Left/Right Knee Randomization to Zip device or staples                             | X                |  |                                   |                                    |  |

|   |   |   |    |   |   |
|---|---|---|----|---|---|
| Photographs Taken   |   |   | X* | X | X |
| Adverse Events/Complications  |   | X | X  | X | X |
| Physician Evaluations (Satisfaction)  |   |   | X  |   | X |
| Physical Therapist Evaluations (ROM)  | X |   |    | X | X |
| Patient Evaluations(Pain, Comfort, Satisfaction)  | X |   | X  | X | X |
| Cosmetic outcome (CVAS, WES)  |   |   |    | X | X |
| Study Exit Form -CRF  |   |   |    |   | X |
| *Optional   |   |   |    |   |   |
| **Final visit will take place between week 6 and week 8 post surgery depending on surgeons standard visit schedule. |   |   |    |   |   |

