#### 9.3 *Sample Size Justification*

Since this is a Bilateral Study, with CVAS scores (Scores: 0 – 10), a paired “t” significant test is the most appropriate test as there is only one variable changing with the patients, i.e., type of closure device. A paired “t” test has more statistical power as well, and is more appropriate since the results will be comparing the treatment and control in a paired fashion.

The targeted minimum sample size of n=22 subjects (paired observations) was determined assuming an average difference ( $\Delta$ ) > 1.0, an hypothesized standard deviation of ~1.5, with the Power of Test set at 90%. Alpha Error for the test of differences = 0.025.

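### The knee that receives Zip is randomised left or right and recorded, but the primary paired t test has no side term; the test is valid, and blocking plus a side term is a cheap gain in precision and conditional error control.

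*Combined protocol and SAP*

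**What the plan says.** Table 1 lists "Left/Right Knee Randomization to Zip device or staples" before the procedure. Section 8.4.2 does this by sealed envelope: Zip goes on one knee and staples on the other. Section 8.2 adds that "Subjects will be randomized in a 1:1 ratio". No section describes blocking or another way of balancing side. Section 8.4.3 requires "Treatment and control sides" to be recorded.

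For the primary endpoint, the CVAS part of Section 9.2.2 specifies: "A 1-sided paired “t” test will be performed", with "Alpha Error for the 1-sided test = 0.025". It mentions neither a side term nor a check for a side effect. Section 9.3 defends the paired test on the ground that closure device is the one thing that differs within a patient.

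Randomisation comes before surgery. Subjects who turn out to need a total replacement on one side and a unicompartmental on the other are then exited and not analysed (Sections 5.1 and 8.4.3), and missing data are left out (Section 9.1.4).

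**The concern.** In every pair, side changes along with closure, so the premise in Section 9.3 is inaccurate. Suppose right and left knees score differently for reasons unrelated to closure. The Zip minus staple differences then centre on one value in Zip-right subjects and another in Zip-left subjects. The plain paired t test pools the two groups, counts the gap between them as noise, and lets any surplus of one side move the mean. The structure is that of a crossover analysed without its period term.

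At stake are some power in a trial of about 22 pairs, and the error rate that applies to the split actually obtained. Even balanced envelopes may not give a balanced analysis set, because of exits after randomisation and missing data.

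**Working it through.** **Inputs.** Section 9.3 gives the sample size "assuming an average difference ( $\Delta$ ) > 1.0" and "an hypothesized standard deviation of ~1.5, with the Power of Test set at 90" per cent, with 22 pairs and alpha 0.025. I use a difference of 1.0 and read 1.5 as the SD of the paired difference, which the document does not state. The left-right effect g is my assumption, shown from 0 to 1.0 CVAS points.

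**1. The plan's own figure.** The normal approximation gives n = (1.5 × (1.960 + 1.282) / 1.0)² = 23.64, so 24, against the stated 22. The exact t calculation gives 26. At n = 22 the noncentrality is 1.0 × √22 / 1.5 = 3.127. With critical t = 2.080 on 21 df, power is 84.6%. This is the g = 0 baseline; its gap to 90% has nothing to do with side.

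**2. Model.** Orient the scale so that positive differences favour Zip. Write d = D + g·s + e, with D = 1.0, SD(e) = 1.5, and s = +1 for Zip on the right knee, −1 for Zip on the left. The side-adjusted estimate is the mean of the two side-group means, which is centred on D whatever g is.

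**3. Power at 11:11.**
- With the side term, SE = (1.5/2) × √(1/11 + 1/11) = 0.320, the same as 1.5/√22. The critical t is 2.086 on 20 df, and power is 84.5% for every g.
- Without it, the spread used by the test rises to about √(1.5² + g²). Power below is simulated; direct numerical integration agrees to about 0.1 point.

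| g | SD used by plain test | Power, plain | Power, side term |
|---|---|---|---|
| 0 | 1.50 | 84.7% | 84.5% |
| 0.25 | 1.52 | 84.0% | 84.5% |
| 0.5 | 1.58 | 81.8% | 84.5% |
| 1.0 | 1.80 | 72.6% | 84.5% |

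**4. Other reading of the SD.** If 1.5 already includes side variation, the residual SD is √(1.5² − g²): 1.48 at g = 0.25 and 1.41 at g = 0.5. At 11:11, power without and with the side term is then about 84.9% and 85.4%, and 85.8% and 88.4%. Nothing is lost against the baseline, and adjustment is a gain.

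**5. Unequal sides.** If allocation is not blocked, the chance of a split of 14:8 or worse in either direction is 2 × P(Bin(22, 0.5) ≥ 14) = 0.286. At 14:8 the plain estimate moves by g × (14 − 8)/22 = 0.27g, that is 0.07, 0.14 or 0.27 points for g = 0.25, 0.5 or 1.0. One-sided type I error given that split:

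| g | Plain, split favours Zip | Plain, split favours staples | Side term |
|---|---|---|---|
| 0.25 | 0.038 | 0.014 | 0.025 |
| 0.5 | 0.050 | 0.007 | 0.025 |
| 1.0 | 0.066 | 0.001 | 0.025 |

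Averaged over simple randomisation, the plain test's error is 0.025 at each of these g and the estimate is unbiased. At exactly 11:11 the plain test is conservative: 0.020 at g = 0.5 and 0.010 at g = 1.0.

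**6. Price of adjusting when g = 0.** At 11:11 the loss is 84.6 − 84.5, about 0.2 points with rounding. If 3 of 25 blocked subjects are exited it is up to about 0.5. Without blocking, the adjusted SE grows with imbalance: at 14:8 it is 0.75 × √(1/14 + 1/8) = 0.332 against 0.320. Adjusted power then averages about 82.7%, a loss of about 2 points, and the side term only pays for itself above about g = 0.35.

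**The case against.** The strongest reply is that randomising side is itself the protection. The plain paired t test keeps its level and is unbiased over randomisation, so it is a legitimate primary analysis. That stands. A reader might infer that the primary test is biased or invalid; the documents do not support this, because the shift in step 5 exists only conditionally on an imbalance that happens to occur.

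Second, nothing in the documents indicates a left-right scar difference of any size. That also stands. The 72.6% figure supposes a side effect as large as the whole planned device effect and adds it on top of the planning SD. It cannot be read as the trial's expected power.

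Third, adjustment can lose power. This is correct for unblocked allocation below about g = 0.35, and it is why the side term should come together with blocking. The documents do not say how the envelope list was made, so the 29% chance of a marked imbalance holds only if the list is unblocked.

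Fourth, one common side coefficient does not remove handedness or operating-order effects that run in different directions for different surgeons, which is possible with up to 3 sites. This too stands and limits what the side term can do.

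None of this restores the Section 9.3 premise, nor does it argue against a blocked design with a prespecified side term at a cost of half a point of power or less.

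**Conclusion.** The concern holds as a matter of precision and conditional error, and the remedy is a cheap improvement rather than a repair of an invalid test. With residual SD 1.5 and balanced sides, omitting side costs about half a point of power at g = 0.25, about 3 points at g = 0.5 and about 12 at g = 1.0, and nothing at g = 0. Given a 14:8 split favouring Zip, the nominal 0.025 becomes 0.038 to 0.066 over g from 0.25 to 1.0; the side term holds it at 0.025.

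These sizes rest on an assumed g, on a difference of 1.0 with 22 analysed pairs, and on reading 1.5 as the SD of the differences net of side. If 1.5 already includes side variation, the benefit is instead a gain of about 0.6 points at g = 0.25 and 2.6 at g = 0.5.

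**What to change.** - Prepare the envelopes in permuted blocks of Zip-left and Zip-right.
- Prespecify the primary analysis as a regression of the within-subject Zip minus staple CVAS difference on side, coded +0.5 and −0.5. Test the intercept one-sided at 0.025. Keep the plain paired t test as a sensitivity analysis.
- Correct the sentence in Section 9.3: side differs within each patient as well as closure.
- If the envelopes cannot be blocked, keep the paired t test as primary and prespecify the side-adjusted model as the sensitivity analysis.

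The cost is some wording, a blocked list, one degree of freedom (critical t 2.080 to 2.086) and about 0.2 to 0.5 points of power if g is zero. No new data, visits or subjects are needed. The choice should be fixed before the split of sides is known, since a side term added after an imbalance is seen would be open to challenge.
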